7.2.1 Key Secondary Outcome Analysis

A key secondary analysis of the ordinal mRS scores will employ a proportional odds model (POM) to test the hypothesis that, among randomized subjects, those who are treated with NA-1 will show a shift in their mRS score distribution at 90 days relative to the mRS distribution of the placebo subjects. The magnitude of the shift will be estimated as the common odds ratio (95% C.I.). Modified Rankin scores of 5 and 6 (bed-bound with severe disability, and death) will be collapsed into a single category representing severely limited functioning. A covariate-adjusted POM will be used to derive the common odds of improvement (i.e. the NA-1 vs. placebo “shift” in mRS score distributions). Model covariates will include all of the variables in the minimization algorithm, both stratification variables and covariates.

The following example SAS code can be used to fit the POM to the subjects’ mRS score:

```
ODS graphics on;
proc logistic data=adqs;
  where ittf1 = 'Y' and qstest = 'mRS (Ordinal)';
  class occloc alteplase thromb_app site
    trtp(param=ref ref='Placebo') ;
  model mRS = age sex blnihss blaspect occloc
    alteplase*thromb_app site trtp;
  effectplot interaction(x=trtp sliceby=mRS)/polybar;
  oddsratio trtp;
run;
```

Where “mRS” is the collapsed mRS scale values ranging from 0 to 5 (level 5 = 5+6 mRS combined), “occloc” is the occlusion location (ICA vs. MCA), “blnihss” is the baseline NIHSS score (0-42), “blaspect” is the baseline ASPECTS score (0-10), ‘alteplase’ is an indicator for having received IV alteplase treatment, thromb_app is the thrombectomy approach (stent retriever vs. aspiration device), alteplase* thromb_app is a 4-level stratification, “site” is investigative site, subject sex and age are the subjects’ sex and age at study entry, and “trtp” is the planned treatment (NA-1, placebo).

When SAS fits the POM, it runs a global test for a shift across all 6 mRS categories in the NA-1 group relative to the placebo; this is the test of the proportional odds (PO) assumption. The proportional odds assumption will be checked via the score test at an alpha-level of 0.15 and also using graphical methods to view the cumulative log odds for each mRS score. If the assumption holds, the POM estimates a single fixed odds ratio for the 5 cumulative binary endpoints defined as follows:

- a. The proportion of subjects with $mRS = 0$ vs. the proportion with $mRS > 0$
- b. The proportion of subjects with $mRS \leq 1$ vs. the proportion with $mRS > 1$**
- c. The proportion of subjects with $mRS \leq 2$ vs. the proportion with $mRS > 2$**
- d. The proportion of subjects with $mRS \leq 3$ vs. the proportion with $mRS > 3$
- e. The proportion of subjects with $mRS \leq 4$ vs. the proportion with $mRS > 4$

This means that regardless of how one chooses to dichotomize the mRS scale, the ratio of the odds of an NA-1-treated subject’s being in the higher functioning category of the dichotomy to a control subject’s odds, will remain the same over the entire span of the mRS scale. Thus, there is no advantage to estimating ORs singly for any of the above dichotomies. If the PO assumption holds, none of them will be significantly different from the common odds ratio. This is analogous to the proportional hazard assumption of the Cox regression model, which posits a constant ratio of treatment vs. control hazard rates at every time point in a study.

Note that the model tests and estimates associated with endpoints “b” and “c” are the more commonly used (and less efficient) mRS dichotomies that represent “good” vs. “poor” functioning. Thus, in addition to providing a statistically powerful test for a treatment vs. placebo shift across all the mRS scores, the POM subsumes the more

common dichotomous mRS analyses that efficacy decisions in stroke trials are often based on (Agresti 2007; Nunn 2016).^[13, 14]

The results of the PO assumption tests, the common odds ratio estimate (with Wald 95% C.I.s) and corresponding Wald test statistics will be summarized in a table. Actual proportions in each category of the collapsed mRS scale with corresponding stacked bar charts will also be presented.

In the event that the test of the PO assumption, needed to proceed with the key secondary efficacy analysis described, determines that the assumption is invalid, this analysis will not be conducted and remaining secondary endpoints to be tested as listed in [Section 7.2.2 to 7.2.5](#) will still be considered to be protected (overall trial alpha still controlled).

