Secondary	Day-90 mRS	Ordinal (0-4,5+6)	ITT	mRS cumulative logits modeled as a function of treatment, baseline ASPECTS, occlusion location, age, sex, baseline NIHSS, alteplase*thromb_app, study site
	Day-90 NIHSS	Binary (≤ 2 vs. > 2)	ITT	logit(binary NIHSS) modeled as a function of treatment, baseline ASPECTS, occlusion location, age, sex, baseline NIHSS, alteplase*thromb_app, study site
	Day-90 Barthel	Binary (< 95 vs. ≥ 95)	ITT	logit(binary Barthel Index) modeled as a function of treatment, baseline ASPECTS, occlusion location, age, sex, baseline NIHSS, alteplase*thromb_app, study site
	Day-90 Mortality	Binary day-90 death status	ITT	logit(binary death status) modeled as a function of treatment, baseline ASPECT, occlusion location, age, sex, baseline NIHSS, alteplase*thromb_app, study site
	Day-90 mRS	mRS Binary (≤ 1 vs. > 1)	ITT	logit(binary mRS) modeled as a function of treatment, baseline ASPECTS, occlusion location, age, sex, baseline NIHSS, alteplase*thromb_app, study site
Tertiary	EQ-VAS	0-100	ITT	EQ-VAS modeled as functions of treatment, baseline ASPECTS, occlusion location, age, sex, baseline NIHSS, alteplase*thromb_app, study site
	Stroke volume	continuous	ITT	Stroke volume (or cubic root transformation of stroke volume) modeled as a function of treatment, baseline ASPECTS, occlusion location, age, sex, baseline NIHSS, alteplase*thromb_app, study site
	BNT15	0-15	ITT	BNT15 Score modeled as a function of treatment, baseline ASPECTS, occlusion location, age, sex, baseline NIHSS, alteplase*thromb_app, study site
	SNAP	0-100	ITT	Total SNAP Score modeled as a function of treatment, baseline ASPECTS, occlusion location, age, sex, baseline NIHSS, alteplase*thromb_app, study site
	MoCA	Binary (< 26 vs. ≥ 26)	ITT	logit(binary MoCA) modeled as a function of treatment, baseline ASPECTS, occlusion location, age, sex, baseline NIHSS, alteplase*thromb_app, study site
	Day-30 mRS	Binary (≤ 2 vs. > 2)	ITT	logit(binary mRS) modeled as a function of treatment, baseline ASPECTS, occlusion location, age, sex, baseline NIHSS, alteplase*thromb_app, study site
Exploratory	Day-90 mRS	Binary (≤ 2 vs. > 2)	ITT	Separate logistic regression models in which the logit(binary mRS) is modeled as a function of treatment only, by each of the subgroups to be considered in the Subgroup forest plots

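### SAP 7.2.1 describes the proportional-odds score test as an NA-1 versus placebo test, but for the specified model it tests all slopes jointly, site included, and its result can cancel the key secondary analysis

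*SAP*

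**What the plan says.** SAP 7.2.1 states that on fitting the model SAS produces a test and that "it runs a global test for a shift across all 6 mRS categories in the NA-1 group relative to the placebo". It adds: "this is the test of the proportional odds (PO) assumption". The rule follows: "The proportional odds assumption will be checked via the score test at an alpha-level of 0.15 and also using graphical methods".

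The illustrative code uses one MODEL statement. Its first line is "model mRS = age sex blnihss blaspect occloc"; the second adds the alteplase-by-device strata, site and treatment. No option or test statement limits the proportional-odds check to treatment. The ordinal row of SAP Table 2 gives the same covariate set: "mRS cumulative logits modeled as a function of treatment, baseline ASPECTS, occlusion location, age, sex, baseline NIHSS, alteplase*thromb_app, study site". The outcome has six levels ("level 5 = 5+6 mRS combined").

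The result is binding. If the test "determines that the assumption is invalid, this analysis will not be conducted". SAP 7.2 and Protocol 11.4 say the same, and both keep the later secondaries protected. SAP 7.2.1 also explains what the assumption means here: the NA-1 to placebo odds ratio is the same wherever the scale is cut.

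**The concern.** Three hypotheses are run together. A shift test asks whether the common NA-1 odds ratio is 1. A proportionality test for NA-1 asks whether its five cut-point odds ratios are equal, which takes 4 df. The default score test asks whether all slopes in the model are equal over the cut-points. The SAP's wording mixes the first two; its code delivers the third.

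This matters because the result decides whether the second test in the fixed sequence is run. A joint test can reject because of a covariate or site although the NA-1 odds ratio is proportional. It can also dilute a real departure in the NA-1 effect over many degrees of freedom. Changing the 0.15 level would not alter which hypothesis is tested.

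**Working it through.** **Inputs.** From SAP 7.2.1: six ordered levels, hence five cut-points; test level 0.15; the model terms. From SAP 1.4: 1076 evaluable subjects. Reading 1076 as the total (538 per arm), 52% against 60.7% at two-sided 0.048 (twice the final one-sided 0.024 in SAP 3.0) gives 81.7% power, which is the stated figure. The documents give no figure for the proportional-odds test beyond its level. They also do not give S, the number of site levels after the pooling in SAP 6.5. I assume 30 to 45 and show 15 to 60.

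**Step 1: degrees of freedom.** The slope parameters are:
- age, sex, NIHSS, ASPECTS and occlusion location: 5
- strata: 3 if coded as the four-level factor the text describes, or 1 if the crossed term without main effects forms only a product column
- site: S - 1
- treatment: 1

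The total is 5 + 3 + (S - 1) + 1 = S + 8, or S + 6 with one stratum parameter. The joint test has (6 - 2) = 4 df per slope parameter:

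| S | 4 x (S + 6) | 4 x (S + 8) | Treatment share, 4 / [4 x (S + 8)] |
|---|---|---|---|
| 15 | 84 | 92 | 4.3% |
| 30 | 144 | 152 | 2.6% |
| 45 | 204 | 212 | 1.9% |
| 60 | 264 | 272 | 1.5% |

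**Step 2: dilution.** Suppose only the NA-1 effect is non-proportional. A departure that the 4-df test detects with 80% power at level 0.15 has noncentrality 8.28; for 95% power it is 14.1. Placing the same noncentrality on the joint df, with three stratum parameters, gives:

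| Power on 4 df | S = 15 | S = 30 | S = 45 | S = 60 |
|---|---|---|---|---|
| 80% | 33% | 29% | 26% | 25% |
| 95% | 48% | 40% | 36% | 33% |

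**Step 3: simulation.** Trials of 1076 subjects were fitted with the adjusted model and tested both ways at 0.15. Set A has 3000 trials per case with 30 and 45 site levels. Set B has 2000 per case with 45 and 20 site levels, shown in that order. The Monte Carlo standard error is at most sqrt(0.25/2000) = 1.1 points. Effect patterns, covariate distributions and the mRS distribution are assumptions.

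| What is non-proportional | Set | Joint test rejects | Treatment-only test rejects |
|---|---|---|---|
| Nothing | A | 16-17% | 14-17% |
| Nothing | B | 15.8%; 15.3% | 14.0%; 15.7% |
| Age, slope per SD 0.35 to 0.75 | A | 33-36% | 14-17% |
| Age as above, and NIHSS by +/-0.2 | A | 47-55% | 14-17% |
| Age, OR per decade 0.82 to 0.55 | B | 42%; 55% | 16%; 16% |
| NIHSS only | B | 35%; 39% | 16%; 16% |
| Site only, SD 0.3 at the extreme cut-points | B | 60%; 70% | 15%; 17% |
| NA-1, OR 1.55 falling to 1.05 | A | 20-23% | 50% |
| NA-1, OR 1.7, 1.55, 1.43, 1.2, 1.0 | B | 26%; 28% | 72%; 74% |
| NA-1, OR 1.75 falling to 0.85 | A | 38-41% | 94% |
| NA-1, OR 1.9, 1.7, 1.43, 1.1, 0.8 | B | 50%; 60% | 99%; 99% |

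In the age, NIHSS and site rows the NA-1 odds ratio is exactly proportional, so the joint test's rejections above about 15% come from the covariates.

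**Step 4: dependence on S.** With no site term the joint test still has 4 x 9 = 36 df. The set B age departure then rejects in 78% of trials, against 14% on the treatment-only test. The direction does not depend on the assumed site count; the size does.

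**The case against.** The code is offered as an example, the prose refers to NA-1 against placebo, and graphs are planned beside the score test. On that view the SAP does not clearly make the joint test the sole deciding check. This stands in part: text and code conflict. But Table 2 carries the same full covariate set, the score test is the only check with a level attached, and the graphs have no decision rule and are not said to be by arm.

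Checking the whole fitted model is also conventional, so part of the choice is preference. That is fair as general practice. Here, though, the SAP explains the assumption as constancy of the NA-1 odds ratio, and the joint test is a weak check of that.

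A reader might infer that a non-proportional NA-1 effect would go unseen. The documents do not support that: cumulative log odds are plotted, proportions in each mRS category are tabulated, and mRS 0-2 and 0-1 are analysed separately. A reader might also infer an inflated type I error. If NA-1 has no effect, its log odds ratio is zero at every cut-point and so is proportional; a missed departure changes how the common odds ratio is interpreted, and no false-positive route has been shown.

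The strongest objection concerns the remedy. With the cancel rule kept, a treatment-only check cancels the key secondary more often when NA-1 is truly non-proportional: 50% against 20-23% where the odds ratio falls from 1.55 to 1.05 and never drops below 1. This stands, and it is a cost of the change.

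**Conclusion.** The sentence in SAP 7.2.1 is wrong: the test it describes is not the one its model produces, and that test decides whether the key secondary is performed. Non-proportional covariate or site effects can cancel the analysis while the NA-1 effect is proportional, though they need not do so. A departure in the NA-1 effect that 4 df would detect with about 95% power is detected by the joint test roughly 36-41% of the time at 144 to 212 df.

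These sizes rest on the assumed site count, slopes and mRS distribution. The df formula and the direction do not depend on the site count. The primary analysis is untouched, and the key secondary is confirmatory only if the primary succeeds. I rate this as should-fix.

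**What to change.** Replace the sentence with an accurate description: the default score test is a joint test of equal slopes for all model parameters and is not a test of shift. Pre-specify the deciding check as the 4-df test that the five `trtp` coefficients are equal. This means a partial proportional-odds model with `UNEQUALSLOPES=trtp`, common slopes for covariates and site, and an explicit equality contrast, because the option alone only estimates the five coefficients. Report the joint score test and the graphs descriptively. State how the strata are coded.

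The cost is SAP wording, one model option and one contrast; no subjects or data are needed. It should be settled before unblinding, since choosing the check afterwards would make the running of a confirmatory analysis data-dependent. The SAP should acknowledge the downside: while the cancel rule is kept, this check removes the key secondary more often when the NA-1 effect is truly non-proportional, and in about 14-17% of trials when it is proportional.

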11.4 Key Secondary Outcome Analysis

The study will also test the secondary hypothesis that among randomized subject, those who are treated with NA-1 will show shift in the distribution of scores on the mRS scale at 90 days, assuming that categories 5 and 6 (bedbound with severe disability, and death) are collapsed. This secondary outcome will use an adjusted proportional odds model to derive the common odds of improvement ("shift") along the mRS scale. Adjustment will include all of the variables in the stratification and minimization algorithm (age, sex, baseline NIHSS score, baseline ASPECTS score, occlusion location, intravenous alteplase treatment, declared first endovascular approach used and site). The proportional odds assumption will be tested.

The choice of the shift analysis is based upon empirical evidence that the mRS scale, when categories 5 and 6 are combined, is a true interval scale meaning that any one step increment in the scale is the same; thus, it is unlikely that the proportional odds assumption will be violated and clinical step changes across the scale are meaningful.⁴² The proportional odds approach to analysis of the mRS scale was applied in the ESCAPE trial.^{3,43} It allows us to include elderly subject (who have a poorer prognosis irrespective of treatment) because a shift from severe to moderate disability will still be recognized as an important outcome.

Figure 2: Projected outcome by mRS category based data from the ESCAPE trial and estimation of NA-1 effect based on the minimal clinically important difference.

Predicted outcomes by mRS category in the control group are from the ESCAPE trial.³ This shows an average 2-3% improvement in outcomes within each mRS category.

If the distribution of subject follows that shown in Figure 2 (i.e. optimally shows a shift across the full scale with common OR 1.32), simulation (n=5000 iterations) demonstrates that the power will be 97.2% to show a common OR of 1.32 with 1076 evaluable subject.

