All tests will be conducted with two-sided level of significance $\alpha = 0.05$. A fixed sequence multiple testing procedure will control the overall experiment-wise error rate for the trial (see below). It pre-specifies that, with all tests conducted at the same pre-specified significance level, the primary endpoint will be tested first and all subsequent tests are considered failed and deemed exploratory if conducted, in the order specified (primary analysis first, key secondary analysis second, etc.), after the first test which fails.: All tests after the first failed test are considered exploratory. For the purpose of clarity, since the key secondary analysis of the ordinal mRS scores will employ a proportional odds model (POM), if the proportional odds assumption fails, this key secondary analysis will not be performed, and the remaining secondary tests will still be considered to be protected.

The fixed sequential order for testing in the ITT trial population is:

- 1) Primary efficacy outcome
- 2) Key secondary outcome analysis (shift analysis using proportional odds model);
- 3) Secondary efficacy endpoints, as specified in the order presented below in [Section 11.5](#).

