7.2 Secondary Efficacy Analyses

Descriptive summaries will be provided for each secondary endpoint in the ITT population. As with the primary endpoint, secondary endpoint analyses will also generally be adjusted for both the stratification variables and covariates used in the minimization algorithm.

All tests will be conducted with two-sided level of significance $\alpha = 0.05$. A fixed sequence multiple testing procedure will control the overall experiment-wise error rate for the trial (see below). It pre-specifies that, with all tests conducted at the same pre-specified significance level, the primary endpoint will be tested first, and all subsequent tests are considered failed and deemed exploratory if conducted, in the order specified (primary analysis first, key secondary analysis second, etc.), after the first test which fails. All tests that follow the first failed test, are considered exploratory. For the purpose of clarity, since the key secondary analysis of the ordinal mRS scores will employ a proportional odds model (POM), if test of the proportional odds assumption shows the assumption to be invalid, this key secondary analysis will not be performed, and the remaining secondary tests will still be considered to be protected.

The secondary endpoints, and the order they are to be tested, are:

1. Shift to reduced functional dependence analyzed across the whole distribution of scores on the mRS at Day 90 or the last rating.

2. Proportion of subjects with good neurological outcome, as defined by a score of 0-2 vs 3 or greater on the NIHSS at Day 90 or the last rating.
3. Proportion of subjects with functional independence in activities of daily living, as defined by a score of ≥ 95 vs 0-90 on the Barthel Index at Day 90 or the last rating.
4. The proportions of control and NA-1 treated subjects who die by study day 90.
5. The proportion of subjects with mRS score of 0-1 at Day 90.

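### A proportional-odds score test at the 15% level can cancel the key secondary shift analysis, and no replacement ordinal analysis is named

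*SAP*

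**What the plan says.** The shift analysis of Day 90 mRS (six categories, 5 and 6 combined) stands second in the fixed testing sequence, directly after the primary endpoint. SAP 7.2.1 attaches a preliminary test to it: "The proportional odds assumption will be checked via the score test at an alpha-level of 0.15". The same sentence adds a second check, for which no threshold is given; the assumption is examined "also using graphical methods to view the cumulative log odds for each mRS score".

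The consequence of failure appears three times:

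- SAP 7.2: "if test of the proportional odds assumption shows the assumption to be invalid, this key secondary analysis will not be performed".
- SAP 7.2.1: "this analysis will not be conducted and remaining secondary endpoints to be tested as listed in" the sections that follow, with overall alpha regarded as still controlled.
- Protocol 11.4: "if the proportional odds assumption fails, this key secondary analysis will not be performed". The protocol gives no alpha level for the check.

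In each place testing moves on to NIHSS, Barthel Index, mortality and mRS 0-1, which stay protected. No other ordinal analysis of the mRS is named.

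Protocol 11.4 expects the check to pass: "it is unlikely that the proportional odds assumption will be violated". SAP 7.2.1 describes what the software tests as follows: "it runs a global test for a shift across all 6 mRS categories in the NA-1 group relative to the placebo". The model in SAP Table 2 has more terms than treatment: "mRS cumulative logits modeled as a function of treatment, baseline ASPECTS, occlusion location, age, sex, baseline NIHSS, alteplase*thromb_app, study site".

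**The concern.** A test at the 0.15 level rejects a true assumption about 15% of the time. If the protocol is right that proportional odds will hold, nearly every cancellation is a false alarm, and a confirmatory endpoint is lost for no reason.

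Three features make this worse:

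- The score test for the printed model is a joint test of equal slopes for all terms. A nuisance covariate can therefore cancel the treatment analysis while the NA-1 effect is perfectly proportional.
- The role of the graphical check is undefined, so whether a confirmatory test is run could become a judgement made on final data.
- The gate is not needed to test the null hypothesis. If NA-1 has no effect, both arms share one mRS distribution and proportionality for treatment holds automatically.

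The stake is avoidable power loss on the second-ranked endpoint. It is also the endpoint the protocol values for detecting improvement among severely disabled patients. The mRS 0-2 and 0-1 dichotomies, the only mRS tests left after cancellation, cannot register a move from severe to moderate disability.

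**Working it through.** **Inputs from the documents.** Gate alpha 0.15 (SAP 7.2.1); shift test two-sided 0.05 (SAP 7.2); common OR 1.32, 1076 evaluable subjects and 97.2% power (protocol 11.4); placebo responder rate 52% and 8.7-point difference (SAP 1.4); final primary boundary 0.024 one-sided (SAP 3.0).

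**Assumed, because the documents do not give them.** Placebo mRS distribution (Figure 2 is not shown), number of sites, covariate effects. The interim look is ignored.

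**1. The plan's own power figure.** A standard approximation (Whitehead) is power = Φ(ln OR × √[N(1 − Σp̄³)/12] − 1.96), where p̄ is the mean category proportion over the two arms. Take placebo 15/20/17/17/13/18%. Applying OR 1.32 to each cumulative odds gives p̄ = 0.169, 0.213, 0.172, 0.164, 0.121, 0.161, so Σp̄³ = 0.030. Then 0.2776 × √(1076 × 0.970/12) − 1.96 = 0.2776 × 9.33 − 1.96 = 0.63, and Φ(0.63) = 73.5%. Other distributions gave 73.2-73.6%. The stated 97.2% is not reproduced; reading 1076 as per group gives about 95.6%. That is a separate matter, but it means the starting point below is about 72%, not 97.2%. On the protocol's own figure, and assuming independence, the gate gives 0.972 × 0.85 = 82.6%.

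**2. What the score test covers.** With 20 sites the model has 6 single terms (treatment, age, sex, NIHSS, ASPECTS, occlusion), 3 stratum terms and 19 site terms, 28 in all. Equal slopes over five cut-points costs 4 df per term: 28 × 4 = 112 df. With 40 sites it is 48 × 4 = 192 df. Treatment contributes only 4 of these.

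**3. How often the gate fires when proportional odds holds exactly.** Simulation of the covariate-adjusted model, placebo 15/20/17/16/15/17%, OR 1.32, equal-sized sites:

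| Sites | Runs | Cancelled |
|---|---|---|
| 20 | 3000 | 14.6% (SE 0.6) |
| 40 | 1500 | 15.6% (SE 0.9) |

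A separate simulation gave 14-17% across 0 to 50 sites; its runs with sites used unequal site sizes.

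**4. Power lost.** The primary test is the adjusted logistic Wald test at one-sided 0.024.

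| Setting | Shift significant, no gate | Run and significant, gated | Primary and shift, no gate | Primary and shift, gated |
|---|---|---|---|---|
| OR 1.32, 20 sites | 71.5% | 61.3% | 52.6% | 44.9% |
| OR 1.32, 40 sites | 72.0% | 61.1% | 50.7% | 43.1% |
| OR 1.43, 20 sites | 89.8% | 77.0% | 74.5% | 63.7% |

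OR 1.43 is the primary design effect: (0.607/0.393)/(0.52/0.48) = 1.43. After a significant primary, the losses are 52.6 − 44.9 = 7.7, 50.7 − 43.1 = 7.6 and 74.5 − 63.7 = 10.8 points.

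**5. What the gate protects.** At OR 1.32, an always-run shift test fails after a significant primary in 2.9% (20 sites) or 3.8% (40 sites) of trials. The gate would have skipped that failing test in 0.3% or 0.9%.

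**6. Cancellation by a nuisance covariate (illustrative).** Treatment is exactly proportional and only age is not, by ±0.10, ±0.15 or ±0.25 log-odds per SD across the five cuts. The global test cancels in 21%, 31% and 63% of trials; a treatment-only 4-df test stays at 15-16%. Nothing in the documents fixes these departures, so they show direction, not a forecast.

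**The case against.** **The documents do not say that p < 0.15 alone cancels the analysis.** A graphical check stands beside the score test, and the protocol states no alpha. This is fair: the 15% follows from one reading. It is the natural one, because both SAP cancellation clauses turn on the test of the assumption and the graphs carry no threshold. The other reading leaves the decision rule undefined, which is itself a defect.

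**The sponsor foresaw failure and prespecified what follows.** Later endpoints stay protected, mRS 0-1 is still tested, and proportions in every mRS category are still reported. This is true, and it is why type I error is not at issue. It does not replace the ordinal test.

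**The joint reading of the test rests on example code.** The prose describes NA-1 against placebo. But Table 2 lists the same full set of terms, and the text says the test is what the software runs when it fits that model. If a treatment-only test was intended, the SAP must say so, and it would still cancel about 15% of the time.

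**The trade-off in step 5 assumes exact proportional odds, where the gate cannot help.** This is the strongest point. Take an unadjusted case with OR 1.43 at the mRS 0, 0-1 and 0-2 cuts and 1.0 at the two worse cuts. An ungated shift test then fails after a significant primary in about 21% of trials. A 4-df gate spares nearly all of those failures; a global test, approximated at 112 df, spares about 12%. But in the same case the 4-df gate discards a significant shift result after a significant primary in about 60% of trials, and the global test discards a significant shift in about a third. The benefit of the gate is therefore larger than 0.3-0.9% when the assumption truly fails, but its cost grows more.

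**Conclusion.** The concern holds. If the score test decides, the key secondary analysis is lost in about 15% of trials in which its assumption is true. That follows from the plan's own alpha and is confirmed by simulation of the planned model (14-17%); it depends little on the assumed sites, covariate effects or mRS distribution.

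The power figures do rest on those assumptions. The chance of a significant primary followed by a significant shift result falls by about 8 points at OR 1.32 and about 11 at OR 1.43. The cancellation rate can be higher if any covariate or site effect is non-proportional, by an amount the documents do not allow one to estimate.

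The primary analysis and type I error are unaffected. This is an avoidable loss on a secondary endpoint, together with an incomplete decision rule and a wrong description of the test. It should be fixed.

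**What to change.** Remove the gate from SAP 7.2, SAP 7.2.1 and protocol 11.4. Suggested text:

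> The prespecified proportional odds model will always be fitted, and its treatment Wald test takes its place in the fixed sequence. A treatment-specific test of proportionality (4 df), the five cumulative odds ratios and the cumulative log-odds plots are diagnostics only and do not change whether the analysis is performed.

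An alternative is to name one covariate-adjusted or stratified rank test (Wilcoxon or win odds) as the confirmatory p-value in all cases, with the common odds ratio as the estimate.

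In either case, correct SAP 7.2.1 to say that the global score test covers equal slopes for all model terms jointly.

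The change needs wording only. There are two costs. When proportionality fails, the common odds ratio must be read as an average over the cut-points. And a shift test that is always run can fail and end protected testing where the present rule would have skipped it: 0.3-0.9% of trials under exact proportional odds at OR 1.32, more often if the assumption truly fails or the shift is smaller.
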